### 11.2 Shipping Procedures

All sample submissions are to be accompanied with an STS shipping manifest.

#### 11.2.1 Submission Schedule

The receiving laboratory is not available to receive shipments over holidays or weekends. Therefore, samples are only to be shipped via overnight courier Sunday through Thursdays (excluding a day before a holiday).

11.2.1.1 The required initial diagnostic tumor tissue materials are to be submitted within four (4) weeks following patient randomization.

11.2.1.2 Peripheral blood samples from multiple patients may be batched and shipped together. The samples are to be shipped as follows:

- Samples shipped at ambient are to be shipped with a cool pack. If collected Monday – Thursday then ship day of collection. Samples collected on Friday or a weekend are to be placed in a refrigerator and shipped Monday.

- Frozen samples are to be shipped on dry ice (5 lbs. minimum). Samples batched in a regular freezer are to be shipped within a month following the draw. Samples stored at < -70°C may be shipped on a quarterly basis.

Rev. 7/15

#### 11.3 ECOG-ACRIN Sample Tracking System

It is **required** that all samples submitted on this trial be entered and tracked using the ECOG-ACRIN Sample Tracking System (STS). The software will allow the use of either 1) an ECOG-ACRIN user-name and password previously assigned (for those already using STS), or 2) a CTSU username and password.

When you are ready to log the collection and/or shipment of the samples required for this study, please access the Sample Tracking System software by clicking <https://webapps.ecog.org/Tst>.

Rev. 6/14

**Important:** Please note that the STS software creates pop-up windows, so you will need to enable pop-ups within your web browser while using the software. A user manual and interactive demo are available by clicking this link: <http://www.ecog.org/general/stsinfo.html> Please take a moment to familiarize yourself with the software prior to using the system.

An STS generated shipping manifest should be shipped with all specimen submissions.

Please direct your questions or comments pertaining to the STS to [[contact]](mailto:[contact]).

#### Study Specific Notes

Generic Specimen Submission Form (#2981v2) will be required only if STS is unavailable at time of sample submission. Notify the laboratory of the shipment

by Faxing a copy of the completed form to the laboratory. Indicate the appropriate Lab on the submission form:

- ECOG-ACRIN CBPF

Retroactively enter all specimen collection and shipping information when STS is available.

#### 11.4 Use of Specimens in Research

Pathology materials will be distributed to investigators for the central diagnostic review and laboratory research studies defined in Section [12](#).

Specimens from patients who consented to allow their specimens to be used for future ECOG-ACRIN-approved research studies will be retained in an ECOG-ACRIN-designated central repository. For this trial, specimens will be retained at the ECOG-ACRIN Central Biorepository and Pathology Facility.

Specimens submitted will be processed to maximize their utility for current and future research projects. Tissue processing may include, but not limited to, extraction of DNA and RNA and construction of tissue microassays (TMAs). DNA and plasma (if appropriate) will be isolated from the submitted peripheral blood samples.

Any residual blocks will be available for purposes of individual patient management on specific written request.

If future use is denied or withdrawn by the patient, the samples will be removed from consideration for use in any future study. Pathology materials may be retained for documentation purposes or returned to the site. All other specimens will be destroyed per guidelines of the respective repository

#### 11.5 Sample Inventory Submission Guidelines

Inventories of all samples submitted from institutions will be tracked via the ECOG-ACRIN STS and receipt and usability verified by the receiving laboratory. Inventories of specimens forwarded and utilized for approved laboratory research studies will be submitted by the investigating laboratories to the ECOG-ACRIN Operations Office – Boston on a monthly basis in an electronic format defined by the ECOG-ACRIN Operations Office – Boston

Rev. 5/15

## 12. Laboratory Research Studies

Submission of tumor tissue for central review and research studies is mandatory (see Section 11). Representative tumor tissue samples will be processed and routed by the ECOG-ACRIN CBPF for use in the studies described below. The results of these studies are for the purposes of the trial only and will not be returned to the site or reported to the patient.

Priority of tissue use:

1. Pathology Review
2. MGMT status by IHC
3. MGMT status by promoter methylation

### 12.1 Pathology Review

The appropriate representative tumor tissue samples will be forwarded to [name] for central diagnostic review and classification to confirm the diagnosis of low or intermediate grade pNET. This is a retrospective review to determine the evaluability of the patient's data for data analysis. The results of the review are for the purpose of the trial only and will not be returned to the site.

### 12.2 Evaluation of MGMT status by IHC

Mouse monoclonal antibody to MGMT will be used (1:25 dilution; clone MT 3.1; Lab Vision), a biotinylated secondary antibody (mouse IgG), and then avidin-horseradish peroxidase (Vectastain Elite ABC Kit; Vector Laboratories) according to the manufacturer's instructions. Immunohistochemical MGMT expression will be scored as either "intact" or "deficient" in tumor cells using a prospective classification scheme. Tumors will be scored as "intact" when there is nuclear staining for MGMT in any tumor cells. Tumors will be scored as "deficient" when there is a complete absence of nuclear staining for MGMT in all tumor cells. Non-neoplastic cells (lymphocytes, stromal cells, and endothelial cells) served as an internal positive control in all tissue sections. We will additionally use an external tissue array control slide with known negative tumor.

The assay will be performed in a CLIA certified lab under the direction of [name] at Stanford University.

### 12.3 Evaluation of MGMT status by promoter methylation

DNA is purified from formalin-fixed paraffin embedded and then treated with bisulfite. Bisulfite treatment chemically converts unmethylated cytosines to uracil but does not affect methylated cytosine. Two PCR reactions are then performed using primers corresponding to bisulfite modified (unmethylated) or unmodified (methylated) MGMT promoter sequence. The products of the PCR reaction are analyzed by agarose gel electrophoresis. Methylation-specific PCR performed on paraffin-embedded tissue specimens is dependent on tissue quality and quantity. It is important that there is little tissue necrosis since amplification could otherwise be compromised. It is to be expected to frequently see amplification of both methylated and unmethylated MGMT promoter sequences in the same specimen, which likely represents heterogeneity among tumor cells and/or the presence in the specimen of non-neoplastic cells. Presence of promoter

methylation, which causes epigenetic silencing of the MGMT gene, a DNA repair gene on chromosome 10q26, is a positive predictive factor for chemotherapeutic response to alkylating agents.

The assay will be performed in a CLIA certified lab under the direction of [name] M.D at Stanford University.

#### 12.4 Statistical Considerations

From prior correlative studies in ECOG-ACRIN it is expected that about 75% of cases will provide tissue amenable to MGMT evaluation, accounting for samples not obtainable and assay yield among obtainable samples. From earlier studies in pancreatic neuroendocrine tumors it is also anticipated that the MGMT-deficiency rate is roughly 50% and MGMT-deficient tumors are expected to be associated with higher levels of objective tumor response to temozolomide based therapy. Assuming that the overall response rate is 41% (across both treatment arms, under the alternative hypothesis) and that roughly 104 eligible patients with samples are available, there will be at least 80% power to detect an absolute difference in response rates of 29% (for example, 55% versus 26% in the MGMT-deficient versus MGMT-intact groups, respectively) using a two-sided 5% level Fisher's exact test. If the true difference in response rates between MGMT-deficient and MGMT-intact tumors is larger, power will be higher (for example 90% power for a difference in response rates of 57% versus 24%) and if the overall treatment response rate is closer to the null hypothesis (overall 33% response rate in both arms), there will be at least 85% power for the same level of absolute response rate difference, 29%, between the MGMT-deficient versus MGMT-intact groups. The evaluation of MGMT by IHC and promoter methylation and correlation with progression-free and overall survival will be exploratory in nature. Furthermore, statistical power for MGMT deficiency by treatment arm interactions will be limited given the relatively small size of this trial and these analyses will also be exploratory.

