With 138 patients there will be at least 80% power to detect an absolute difference of 20% in the objective response rates (for example, between 33% and 53% true response rates) using a two-group Fisher's exact test at an overall two-sided 20% significance level. In addition, within each arm, a 90% confidence interval on the true objective response rate will be no wider than 21 percentage points. Overall survival will also be a secondary endpoint but power for overall survival comparisons will be limited.

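### The MGMT-response test in 12.4 pools the arms; stratifying it by arm is a minor, no-cost improvement that removes the effect of chance MGMT-by-arm imbalance

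*Combined protocol and SAP*

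**What the plan says.** Section 12.4 expects that "about 75% of cases will provide tissue amenable to MGMT evaluation" and takes "roughly 104 eligible patients with samples are available". About half of the tumors are expected to be MGMT-deficient. The main case is "55% versus 26% in the MGMT-deficient versus MGMT-intact groups", a 29-point difference, for which at least 80% power is claimed "using a two-sided 5% level Fisher's exact test". Two further claims follow: 90% power for 57% versus 24%, and at least 85% for a 29-point difference when response is 33% in both arms.

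The main case rests on a single pooled rate: "overall response rate is 41% (across both treatment arms, under the alternative hypothesis"). Arm enters 12.4 only through MGMT-by-arm interaction analyses, which are labelled exploratory.

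Section 9.3 powers the response comparison between arms on a 20-point difference, for example "between 33% and 53% true response rates". The randomization strata in 4.5 and 9.2 are prior everolimus, prior sunitinib and concurrent octreotide. MGMT status is not among them. Section 11 specifies previously collected tissue, so MGMT status is a baseline factor that trial treatment cannot change.

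**The concern.** If the combination raises response by 16 to 20 points, arm is a known predictor of the outcome in the MGMT analysis. The balance of MGMT-deficient tumors between arms in about 104 patients is left to chance. If more of the deficient tumors fall in the combination arm, the crude MGMT difference picks up part of the arm effect and looks too large; if fewer do, it looks too small. The unused arm effect also adds some variation to the pooled comparison.

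MGMT as a predictor of response is a listed secondary objective (2.2.4), and section 1.2 says a positive association could support using MGMT expression to decide who receives temozolomide-based treatment. It is therefore worth having an estimate that does not depend on how MGMT status happened to fall between the arms.

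**Working it through.** **1. The plan's own figures.** Inputs from 12.4: 0.75 × 138 = 103.5, so 104 patients, and 50% deficient, so 52 versus 52. Exact power of the two-sided 5% Fisher test, by full enumeration of two binomials:

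| Response, deficient vs intact | Stated | Recomputed |
|---|---|---|
| 55% vs 26% | at least 80% | 83.1% |
| 57% vs 24% | 90% | 92.0% |
| 47.5% vs 18.5% (33% overall) | at least 85% | 85.1% |

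All three reproduce.

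**2. Size of the arm difference.** Section 9.3 gives 53 − 33 = 20 points. Those rates average (33 + 53)/2 = 43%, whereas 12.4 uses 41%. Holding temozolomide at 33%, 41% implies 2 × 41 − 33 = 49% on the combination, a gap of 16 points. Hence the range of 16 to 20.

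**3. Shift from chance imbalance.** Assume 52 patients per arm with MGMT results. The difference between arms in the share of deficient tumors has mean 0 and

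SD = √(0.25/52 + 0.25/52) = 0.098.

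The crude MGMT difference moves by (arm difference) × (imbalance in share):

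- Typical (1 SD): 0.20 × 0.098 = 2.0 points; with a 16-point gap, 0.16 × 0.098 = 1.6 points.
- 28 versus 24 deficient: 0.20 × 4/52 = 1.5 points.
- 31 versus 21 deficient (0.192/0.098, about 2 SD, roughly 1 trial in 20): 0.20 × 10/52 = 3.8 points; with a 16-point gap, 3.1 points.

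**4. Average power.** Simulation with 52 per arm, MGMT status random within arm at 50%, and response of 45%/16% (temozolomide, deficient/intact) and 65%/36% (combination):

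| | Pooled | Arm-stratified | Gain |
|---|---|---|---|
| Exact tests | 84.7% | 85.4% | 0.7 |
| Asymptotic tests (chi-square, CMH) | 86.2% | 87.6% | 1.4 |

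With a 16-point arm gap the gains are 0.5 points (84.2% to 84.7%) and 0.9 points (85.7% to 86.6%).

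**5. Power given the imbalance obtained.** Same response rates, 31 versus 21 deficient per arm:

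| Excess of deficient tumors in | Pooled Fisher | Stratified exact | CMH |
|---|---|---|---|
| Temozolomide arm | 71.3% | 83.9% | 87.0% |
| Combination arm | 92.3% | 84.9% | 87.0% |

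**6. Type I error.** No MGMT effect, 20-point arm effect, MGMT random within arm: pooled Fisher 4.2%, stratified exact 4.0%, CMH 4.9%. At a fixed 21 versus 31 split, pooled Fisher is at 4.8%.

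**The case against.** The case for leaving 12.4 alone is strong in several respects. Nothing in the section fails: the named test delivers the stated power, and a pooled question fits objective 2.2.4, which covers patients treated with either regimen. The 20-point arm difference is only an example used for powering. If the arms do not differ, stratifying gains nothing (84.3% for pooled Fisher, 84.0% for the stratified exact test). The planned interaction analyses would also let an imbalance be seen. All of this stands, and it limits the point to a refinement.

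A reader might infer three stronger things that the documents do not support.

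- **That pooling biases or confounds the MGMT comparison.** Tissue predates the trial and allocation is randomized 1:1, so MGMT status is independent of arm in expectation. The 2 points is the SD of a mean-zero shift, and type I error stays below 5% on average.
- **That stratifying buys about 3 points of power.** A gap that large appears only when the exact pooled test is set against the asymptotic CMH test. Part of it comes from Fisher's conservatism, which the exact stratified test shares.
- **That arm is the strongest predictor the plan assumes.** The plan assumes 29 points for MGMT and at most 20 for arm.

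The objection does not answer the dependence on the sample obtained. At a 2-SD imbalance, power of the pooled test differs by about 21 points (92.3 − 71.3) according to which arm holds the excess, while each stratified test stays within about 1 point of itself. Interaction tests with limited power do not supply an adjusted main estimate.

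**Conclusion.** The point holds as a minor, free improvement. Section 12.4 specifies only a pooled test, although the plan's alternative includes an arm difference of 16 to 20 points and MGMT status is not balanced by design. The cost of pooling is about 1 point of power like for like, and a chance shift in the crude MGMT difference with an SD of about 2 points, reaching about 4 points in roughly 1 trial in 20. Against a 29-point effect this would seldom change the conclusion. The MGMT analysis is not invalid, and the 80%, 90% and 85% claims stand.

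The figures assume 52 patients per arm with MGMT results, a 50% deficiency rate in each arm, and no MGMT-by-arm interaction on the risk-difference scale. A logit-additive model gave nearly the same results: 84.1% versus 84.9% for the exact tests and 85.7% versus 87.1% for the asymptotic ones.

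**What to change.** In 12.4, make the main MGMT-response test one stratified by treatment arm. Use the exact stratified (conditional) test if strict type I control is wanted, or CMH if asymptotic control is accepted, and name the choice in advance. Report the arm-stratified odds ratio or risk difference with its confidence interval. Leave the interaction analyses exploratory.

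The power paragraph needs no new sample size. The claim of at least 80% holds for either stratified test (85.4% exact, 87.6% CMH in the main case), with a note that it was computed for the unstratified test.

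The cost is one or two sentences and no new data, since arm is recorded for every patient. CMH gives up strict exactness; the exact version keeps it with a smaller gain. Specifying the test now also avoids a later choice between crude and adjusted results if an imbalance appears.

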#### 12.5 Lab Data Transfer Guidelines

The data collected on the above mentioned laboratory research studies will be submitted electronically using a secured data transfer to the ECOG-ACRIN Operations Office – Boston by the investigating laboratories on a quarterly basis or per joint agreement between ECOG-ACRIN and the investigator. The quarterly cut-off dates are March 31, June 30, September 30, and December 31. Data is due at the ECOG-ACRIN Operations Office – Boston 1 week after these cut-off dates

### **13. Electronic Data Capture**

Please refer to the E2211 Forms Completion Guidelines for the forms submission schedule. Data collection will be performed exclusively in Medidata Rave.

This study will be monitored by the CTEP Data Update System (CDUS) version 3.0. Cumulative CDUS data will be submitted quarterly from the ECOG-ACRIN Operations Office – Boston to CTEP by electronic means.

### **14. Patient Consent and Peer Judgment**

Current FDA, NCI, state, federal and institutional regulations concerning informed consent will be followed.

**Appendix I**

**Pathology Submission Guidelines**

The following items are included in Appendix I:

1. Guidelines for Submission of Pathology Materials  
(instructional sheet for Clinical Research Associates [CRAs])
2. Instructional memo to submitting pathologists
3. List of Required Materials for E2211
4. ECOG-ACRIN Generic Specimen Submission Form (#2981)

## Guidelines for Submission of Pathology Materials

The following items should always be included when submitting pathology materials to the ECOG-ACRIN Central Biorepository and Pathology Facility:

- Institutional Surgical Pathology Report
- Pathology materials (see attached List of Required Material)
- ECOG-ACRIN Generic Specimen Submission Form (#2981)

### Instructions:

1. Submitted materials must be adequately labeled, including:  
Patient's name (last, first)  
Protocol number  
Protocol case number (the patient's ECOG-ACRIN sequence number)  
Institution
2. Complete blank areas of the pathologist's instructional memo and forward it, along with the List of Required Material and, if used, the Generic Specimen Submission Form, to the appropriate pathologist.
3. The pathologist should return the required pathology samples and surgical pathology reports, along with the completed ECOG-ACRIN Generic Specimen Submission Form (#2981). If any other reports are required, they should be obtained from the appropriate department at this time.
4. Keep a copy of the submitted documents and the StS-generated shipping manifest for your records.
5. Double-check that ALL required forms, reports and pathology samples are included in the package to the Central Biorepository and Pathology Facility. (See appropriate List of Required Material.)

**Pathology specimens submitted WILL NOT be processed by the Central Biorepository and Pathology Facility until all necessary items are received.**

Mail pathology materials to:

ECOG-ACRIN Central Biorepository and Pathology Facility  
MD Anderson Cancer Center  
Department of Pathology, Unit 085  
Tissue Qualification Laboratory for ECOG-ACRIN, Room G1.3586  
[name]  
[name]  
Phone: Toll Free [name] [contact] Local or International Sites)  
[contact]  
Email: [[contact]](mailto:[contact])

If you have any questions concerning the above instructions or if you anticipate any problems in meeting the pathology material submission deadline of one month, contact the Pathology Coordinator at the ECOG-ACRIN Central Biorepository and Pathology Facility by [contact] or by email at [[contact]](mailto:[contact]).

Rev. 5/15

## List of Required Material

E2211: A Randomized Phase II Study of Temozolomide or Temozolomide and Capecitabine in Patients with Advanced Pancreatic Neuroendocrine Tumor

### Pre-Treatment

1. Institutional pathology report (**must be included with EVERY pathology submission**).
2. Institutional surgical report (if surgical materials are submitted) and immunological studies reports (if performed)
3. *ECOG-ACRIN Sample Tracking System (STS) generated shipping manifest*
4. Required path materials.
  - All original stained diagnostic slides.

Rev. 6/14

**NOTE:** These slides will be returned to the site upon completion of the review which is retrospective and will be performed in batches. If the return of these slides is to be expedited:

1. Contact the repository to discuss expedited review. They may request that materials be held until requested.
2. Upon submission, indicate need for expedited review on the 638 form AND in the appropriate comment field in STS.
3. If submission is delayed, a copy of the applicable reports (#2 and #3 above) must be submitted and it is requested that the delay to submit the materials be indicated in STS.

- One representative diagnostic formalin-fixed paraffin-embedded **tumor block**, core biopsy or surgical specimen preferred.

**NOTE:** If a block is unavailable for submission, submit the following:

- Twenty (20) unstained slides 4 $\mu$ m thick
- Two (2) 4mm cores.

If these criteria cannot be met, please contact the ECOG-ACRIN Central Biorepository and Pathology Facility (CBPF) ([[contact]](mailto:[contact])) to obtain alternative submission requirements.

**NOTE:** Since blocks are being used for laboratory studies, in some cases the material may be depleted, and, therefore, the block may not be returned.

[name], and [name], PhD  
Group Co-Chairs

Rev. 5/15

## MEMORANDUM

**TO:** \_\_\_\_\_  
(Submitting Pathologist)

**FROM:** [name]., Chair  
ECOG-ACRIN Laboratory Science and Pathology Committee

**DATE:** \_\_\_\_\_

**SUBJECT:** *Submission of Pathology Materials for E2211: A Randomized Phase II Study of Temozolomide or Temozolomide and Capecitabine in Patients with Advanced Pancreatic Neuroendocrine Tumor)*

The patient named on the attached request has been entered onto an ECOG-ACRIN protocol by \_\_\_\_\_ (ECOG-ACRIN Investigator). This protocol requires the submission of pathology materials for pathology review and laboratory research studies.

Keep a copy of the submission for your records and return, the surgical pathology report(s), the slides and/or blocks and any other required material (see List of Required Material) to the Clinical Research Associate (CRA). The CRA will forward all required pathology material to the ECOG-ACRIN ACRIN Central Biorepository and Pathology Facility.

Blocks and slides submitted for this study will be retained at the ECOG-ACRIN Central Repository for future studies. Paraffin blocks will be returned for purposes of patient management upon written request. The original stained diagnostic slides will be returned upon completion of the review.

*Please note: Since blocks are being used for laboratory studies, in some cases the material may be depleted, and, therefore, the block may not be returned.*

If you have any questions regarding this request, please contact the Central Biorepository and Pathology Facility at [contact] or by email at [[contact]](mailto:[contact]).

The ECOG-ACRIN CRA at your institution is:

Name: \_\_\_\_\_

Address: \_\_\_\_\_

Phone: \_\_\_\_\_

Thank you.

